Hyperuricemia (uric acid)	7.5 to 10.0 mg/dL	10.1 to 12.0 mg/dL	12.1 to 15.0 mg/dL	>15.0 mg/dL
Creatinine	1.1 to 1.5 x ULN	1.6 to 3.0 x ULN	3.1 to 6.0 x ULN	>6 x ULN or dialysis required

Rx=therapy; ULN=upper limit of normal.

ENZYMES				
	Grade 1	Grade 2	Grade 3	Grade 4
Aspartate aminotransferase (AST)	1.1 to <2.0 x ULN	2.0 to <3.0 x ULN	3.0 to 8.0 x ULN	>8.0 x ULN
Alanine aminotransferase (ALT)	1.1 to <2.0 x ULN	2.0 to <3.0 x ULN	3.0 to 8.0 x ULN	>8.0 x ULN
Gamma to glutamyl transferase (GGT)	1.1 to <2.0 x ULN	2.0 to <3.0 x ULN	3.0 to 8.0 x ULN	>8.0 x ULN
Alkaline Phosphatase	1.1 to <2.0 x ULN	2.0 to <3.0 x ULN	3.0 to 8.0 x ULN	>8.0 x ULN
Amylase	1.1 to 1.5 x ULN	1.6 to 2.0 x ULN	2.1 to 5.0 x ULN	>5.1 x ULN
Lipase	1.1 to 1.5 x ULN	1.6 to 2.0 x ULN	2.1 to 5.0 x ULN	>5.1 x ULN

ULN=upper limit of normal.

URINALYSIS				
	Grade 1	Grade 2	Grade 3	Grade 4
Proteinuria	1+ or 200 mg to 1 gm loss/day	2 to 3+ or 1 to 2 gm loss/day	4+ or 2 to 3.5 gm loss/day	Nephrotic syndrome or >3.5 gm loss/day
Hematuria	Microscopic only <10 RBC/HPF	Gross, no clots >10 RBC/HPF	Gross, with or without clots, or red blood cells casts	Obstructive or required transfusion

HPF=high powered field; RBC=red blood cells.

CARDIOVASCULAR				
	Grade 1	Grade 2	Grade 3	Grade 4
Cardiac rhythm	N/A	Asymptomatic, transient signs, no Rx required	Recurrent/persistent; symptomatic Rx required	Unstable dysrhythmia; hospitalization and treatment required
Hypertension	Transient increase >20 mm/Hg; no treatment	Recurrent, chronic increase >20 mm/Hg; treatment required	Acute treatment required; outpatient treatment or hospitalization possible	End organ damage or hospitalization required
Hypotension	Transient orthostatic hypotension with heart rate increased by <20 beat/min or decreased by <10 mmHg systolic BP. No treatment required	Symptoms due to orthostatic hypotension or BP decreased by <20 mmHg systolic; correctable with oral fluid treatment	Requires IV fluids; no hospitalization required	Mean arterial pressure <60 mmHg or end organ damage or shock; requires hospitalization and vasopressor treatment
Pericarditis	Minimal effusion	Mild/moderate asymptomatic effusion, no treatment	Symptomatic effusion; pain; EKG changes	Tamponade; pericardiocentesis or surgery required
Hemorrhage, Blood Loss	Microscopic/occult	Mild, no transfusion	Gross blood loss; 1 to 2 units transfused	Massive blood loss; >3 units transfused

BP=blood pressure; IV=intravenous; EKG=electrocardiogram; N/A=not applicable; Rx=therapy.

RESPIRATORY				
	Grade 1	Grade 2	Grade 3	Grade 4
Cough	Transient; no treatment	Persistent cough; treatment responsive	Paroxysmal cough; uncontrolled with treatment	N/A
Bronchospasm, Acute	Transient; no treatment; FEV ₁ 70 to 80% of peak flow	Requires treatment; normalizes with bronchodilator; FEV ₁ 50 to 70% of peak flow	No normalization with bronchodilator; FEV ₁ 25 to 50% of peak flow; or retractions present	Cyanosis: FEV ₁ <25% of peak flow; or intubation necessary
Dyspnea	Dyspnea on exertion	Dyspnea with normal activity	Dyspnea at rest	Dyspnea requiring oxygen therapy

FEV₁=forced expiratory volume in 1 second; N/A=not applicable.

GASTROINTESTINAL				
	Grade 1	Grade 2	Grade 3	Grade 4
Nausea	Mild or transient; maintains reasonable intake	Moderate discomfort; intake decreased significantly; some activity limited	No significant intake; requires IV fluids	Hospitalization required
Vomiting	1 episode in 24 hours	2 to 5 episodes in 24 hours	>6 episodes in 24 hours or needing IV fluids	Physiologic consequences requiring hospitalization or requiring parenteral nutrition
Constipation	Requiring stool softener or dietary modification	Requiring laxatives	Obstipation requiring manual evacuation or enema	Obstruction or toxic megacolon
Diarrhea	Mild or transient; 3 to 4 loose stools/day or mild diarrhea lasting <1 week	Moderate or persistent; 5 to 7 loose stools/day or diarrhea lasting >1 week	>7 loose stools/day or bloody diarrhea; or orthostatic hypotension or electrolyte imbalance or >2L IV fluids required	Hypotensive shock or physiologic consequences requiring hospitalization
Oral discomfort/ Dysphagia	Mild discomfort; no difficulty swallowing	Some limits on eating/drinking	Eating/talking very limited; unable to swallow solid foods	Unable to drink fluids; requires IV fluids

IV=intravenous.

NEUROLOGICAL				
	Grade 1	Grade 2	Grade 3	Grade 4
Neuro-Cerebellar	Slight incoordination dysdiadochokinesis	Intention tremor, dysmetria, slurred speech; nystagmus	Locomotor ataxia	Incapacitated
Psychiatric	Mild anxiety or depression	Moderate anxiety or depression; therapy required; change in normal routine	Severe mood changes requiring therapy; or suicidal ideation; or aggressive ideation	Acute psychosis requiring hospitalization; or suicidal gesture/attempt or hallucinations
Muscle strength	Subjective weakness; no objective symptoms/signs	Mild objective signs/symptoms; no decrease in function	Objective weakness; function limited	Paralysis
Paresthesia (burning, tingling, etc.)	Mild discomfort; no treatment required	Moderate discomfort; non- narcotic analgesia required	Severe discomfort; or narcotic analgesia required with symptomatic improvement	Incapacitating; or not responsive to narcotic analgesia
Neurosensory	Mild impairment in sensation (decreased sensation, e.g., vibratory, pinprick, hot/cold in great toes) in focal area or symmetrical distribution; or	Moderate impairment (moderately decreased sensation, e.g., vibratory, pinprick, hot/cold to ankles) and/or joint position or	Severe impairment (decreased or loss of sensation to knees or wrists) or loss of sensation of at least moderate degree in multiple different body areas (i.e., upper and lower extremities)	Sensory loss involves limbs and trunk; paralysis; or seizures

	change in taste, smell, vision, and/or hearing	mild impairment that is not symmetrical		
MUSCULOSKELETAL				
	Grade 1	Grade 2	Grade 3	Grade 4
Arthralgia (joint pain)	Mild pain not interfering with function	Moderate pain, analgesics and/or pain interfering with function but not with ADL	Severe pain; pain and/or analgesics interfering with ADL	Disabling pain
Arthritis	Mild pain with inflammation, erythema or joint swelling, but not interfering with function	Moderate pain with inflammation, erythema or joint swelling; interfering with function but not with ADL	Severe pain with inflammation, erythema or joint swelling, and interfering with ADL	Permanent and/or disabling joint destruction
Myalgia	Myalgia with no limitation of activity	Muscle tenderness (at other than injection site) or with moderate impairment of activity	Severe muscle tenderness with marked impairment of activity	Frank myonecrosis

ADL=activities of daily living.

SKIN				
	Grade 1	Grade 2	Grade 3	Grade 4
Mucocutaneous	Erythema; pruritus	Diffuse, maculo papular rash, dry desquamation	Vesiculation or moist desquamation or ulceration	Exfoliative dermatitis, mucous membrane involvement or erythema, multiforme or suspected Stevens-Johnson or necrosis requiring surgery
Induration	<15 mm	15 to 30 mm	>30 mm	N/A
Erythema	<15 mm	15 to 30 mm	>30 mm	N/A
Edema	<15 mm	15 to 30 mm	>30 mm	N/A
Rash at injection site	<15 mm	15 to 30 mm	>30 mm	N/A
Pruritus	Slight itching at injection site	Moderate itching at injection extremity	Itching over entire body	N/A

N/A=not applicable.

SYSTEMIC				
	Grade 1	Grade 2	Grade 3	Grade 4
Allergic reaction	Pruritus without rash	Localized urticarial	Generalized urticarial; angioedema	Anaphylaxis
Headache	Mild, no treatment required	Transient, moderate; treatment required	Severe; responds to initial narcotic therapy	Intractable; requires repeated narcotic therapy
Fever: oral	37.7 to 38.5°C or 100.0 to 101.5°F	38.6 to 39.5°C or 101.6 to 102.9°F	39.6 to 40.5°C or 103 to 105°F	>40°C or >105°F
Fatigue	Normal activity reduced <48 hours	Normal activity decreased 25 to 50%; >48 hours	Normal activity decreased >50%; cannot work	Unable to care for self

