 - Demographic data such as year of birth, sex, sexual orientation, race, and ethnicity will be recorded in the participant's eCRF. The collection of sex, sexual orientation, race, and ethnicity data is necessary to assess and monitor the diversity of the trial participants, and to determine if the trial participants are truly representative of the impacted population. The year of birth is collected to stratify the population.
 - The participant's medical/surgical history will be obtained by interviewing the participant and/or the participant's legally authorized representative and/or review of the participant's medical records. Any pre-existing conditions, signs and/or symptoms present prior to the first dose of study treatment will be recorded in the eCRF.
 - Pretreatment baseline specimens for microbiological testing will be collected as described in Section 9.1 and Table 2.
 - Following completion of all pretreatment assessments, eligible participants will be randomly assigned to treatment as described in Section 7.3.
 - The first oral gepotidacin dose (3000 mg) or the IM ceftriaxone dose (500 mg) plus the oral azithromycin dose (1 g) will be administered at the study site. Oral study treatment (gepotidacin and azithromycin) should be taken after food consumption and with water to assist with tolerability. After dose administration, Day 1 posttreatment assessments will be performed, as shown in Table 1. Any AEs or clinically significant changes should be followed accordingly.
 - Participants randomly assigned to gepotidacin will self-administer the second 3000-mg oral dose as an outpatient 10 to 12 hours after the first dose; however, for participants who weigh <50 kg or have moderate renal impairment, the second dose should be taken approximately 12 hours after the first dose. Gepotidacin study treatment should be taken after food consumption and with water to assist with tolerability. **Note:** The second dose may occur on Day 1 or Day 2, depending on the time at which the first dose was taken. Participants randomly assigned to gepotidacin will be contacted to confirm that they took their second gepotidacin dose (see Section 7.6).

- The TOC and Follow-up Visits should be scheduled before the participant leaves the study site on Day 1 (as indicated in Table 1); the planned return day/time should be at the convenience of the participant and also the availability of the study site staff.

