9.2.1. Time Period and Frequency for Collecting AE and SAE Information

- All SAEs will be collected from the signing of the ICF until the Follow-up Visit at the time points specified in Table 1 (Section 2).
- All AEs will be collected from the start of treatment until the Follow-up Visit at the time points specified in Table 1 (Section 2).
- Medical occurrences that begin before the start of study treatment but after obtaining informed consent will be recorded on the medical history/current medical conditions section of the eCRF and not the AE section.
- All SAEs will be recorded and reported to the sponsor or designee immediately and under no circumstances should this exceed 24 hours, as indicated in Appendix 4. The

investigator will submit any updated SAE data to the sponsor within 24 hours of it being available.

- Investigators are not obligated to actively seek AEs or SAEs in former study participants. However, if the investigator learns of any SAE, including a death, at any time after a participant has been discharged from the study, and he or she considers the event to be reasonably related to the study treatment or study participation, the investigator must promptly notify the sponsor.
- The method of recording, evaluating, and assessing causality of AEs and SAEs and the procedures for completing and transmitting SAE reports are provided in Appendix 4.

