GSK or its designee reserves the right to close the study site or terminate the study at any time for any reason at the sole discretion of GSK. Study sites will be closed upon study completion. A study site is considered closed when all required documents and study supplies have been collected and a study-site closure visit has been performed.

The investigator may initiate study-site closure at any time, provided there is reasonable cause and sufficient notice is given in advance of the intended termination.

Reasons for the early closure of a study site by the sponsor or investigator may include but are not limited to:

- Failure of the investigator to comply with the protocol, the requirements of the IRB/IEC or local health authorities, the sponsor's procedures, or GCP guidelines
- Inadequate recruitment of participants by the investigator
- Discontinuation of further study treatment development
- Total number of participants included earlier than expected

If the study is prematurely terminated or temporarily suspended, the sponsor shall promptly inform the investigators, the IECs/IRBs, the regulatory authorities, and any contract research organization(s) used in the study of the reason for termination or temporary suspension, as specified by the applicable regulatory requirements. The investigator shall promptly inform the participant and should assure appropriate participant therapy and/or follow-up.

12.4. Appendix 4: Adverse Events: Definitions and Procedures for Recording, Evaluating, Follow-up, and Reporting

Definition of Adverse Event

Adverse Event Definition

 An adverse event (AE) is any untoward medical occurrence in a clinical study participant, temporally associated with the use of a study treatment, whether or not considered related to the study treatment. 
NOTE: An AE can therefore be any unfavorable and unintended sign (including an abnormal laboratory finding), symptom, or disease (new or exacerbated) temporally associated with the use of a study treatment.
 
 A treatment-emergent AE is an event that emerges during treatment having been absent pretreatment or worsens relative to the pretreatment state.

Events Meeting the AE Definition

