
 Any abnormal laboratory test results (hematology, clinical chemistry, or urinalysis) or other safety assessments (e.g., electrocardiograms, radiological scans, vital signs measurements), including those that worsen from baseline, considered clinically significant in the medical and scientific judgment of the investigator (i.e., not related to progression of underlying disease). Exacerbation of a chronic or intermittent pre-existing condition including either an increase in frequency and/or intensity of the condition. New conditions detected or diagnosed after study treatment administration even though it may have been present before the start of the study. Signs, symptoms, or the clinical sequelae of a suspected drug-drug interaction. Signs, symptoms, or the clinical sequelae of a suspected overdose of either study treatment or a concomitant medication. Overdose per se will not be reported as an AE/serious AE (SAE) unless it is an intentional overdose taken with possible suicidal/self-harming intent. Such overdoses should be reported regardless of sequelae. “Lack of efficacy” or “failure of expected pharmacological action” per se will not be reported as an AE or SAE. Such instances will be captured in the efficacy assessments. However, the signs, symptoms, and/or clinical sequelae resulting from lack of efficacy will be reported as AE or SAE if they fulfill the definition of an AE or SAE.

Events **NOT** Meeting the AE Definition

- Any clinically significant abnormal laboratory findings or other abnormal safety assessments which are associated with the underlying disease, unless judged by the investigator to be more severe than expected for the participant's condition.
- The disease/disorder being studied or expected progression, signs, or symptoms of the disease/disorder being studied, unless more severe than expected for the participant's condition.
- Medical or surgical procedure (e.g., endoscopy, appendectomy): the condition that leads to the procedure is the AE.
- Situations in which an untoward medical occurrence did not occur (social and/or convenience admission to a hospital).
- Anticipated day-to-day fluctuations of pre-existing disease(s) or condition(s) present or detected at the start of the study that do not worsen.

Definition of an SAE

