8.1. Adverse Events Analyses

All AEs will be collected from the start of treatment until the FU visit and all SAEs will be collected from the signing of the informed consent form until the FU visit based on the timepoints specified in Appendix 1. All reported AEs will be coded using Medical Dictionary for Regulatory Activities (MedDRA) and summarized by system organ class (SOC) and preferred term (PT).

A treatment emergent AE (TEAE) is defined as an AE with start date/time after the first dose date/time of the study treatment. If the time part is missing, only dates will be considered. The number and percentage of TEAEs, study treatment-related AEs, non-serious drug-related AEs, SAEs, and AEs leading to study treatment or study withdrawal will be provided. Any AE starting before the first dose date/time will not be included in any summary analyses but will be displayed in the listings. Therefore, only TEAEs will be included in summary tables with all AEs displayed in listings.

The severity of AEs and SAEs will be determined by the investigator according to the US National Institute of Allergy and Infectious Diseases Division of Microbiology and Infectious Diseases (DMID) criteria for adult toxicity assessment, except for serum creatinine adolescent laboratory data, which will be assessed using DMID pediatric toxicity criteria. Adverse event severity is classified as mild (Grade 1), moderate (Grade 2), severe (Grade 3), potentially life-threatening (Grade 4), or resulting in death (Grade 5). Adverse events starting after the first dose of study treatment with a missing severity will be classified as severe. If a participant reports an AE more than once within the same SOC/PT, the AE with the worst-case severity will be used in the corresponding severity summaries.

The relationship to study treatment, as indicated by the investigator, is classified as “not related” or “related”. Adverse events with a missing relationship to study treatment will be regarded as “related” to study treatment. If a participant reports the same AE more than once within an SOC/PT, the AE with the worst-case relationship to study treatment will be used in the corresponding relationship summaries.

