8.5.2. Quantitative Screening for Identification of Potential ARs

Frequentist approach to screen for potential ARs will be used. Specifically, the Crowe method [Crowe B, et al, 2013] will be applied for initial screening of the large number of adverse events to generate a “short list” of potential ARs. This method is based on three measures:

- Absolute incidence rate (%) in control arm (ceftriaxone plus azithromycin),
- Estimate of treatment effect (Relative Risk [RR]) relative to active control arm (ceftriaxone plus azithromycin),
- An estimate of variability around the treatment effect (95% CI for RR).

High Level Terms (HLTs) will be used to group adverse events and the screening for potential ARs will be conducted at HLT level. Quantitative screening criteria for potential ARs endorsed by the Safety Review Team (SRT) are displayed in the following table:

Criterion	Absolute Incidence in ceftriaxone plus oral azithromycin	HLT RR (Gepotidacin vs ceftriaxone plus azithromycin)	95% CI for HLT RR*
1	No conditions	No conditions	Lower CI > 1
2	≥5%	≥1.25	No conditions
3	<5%	≥1.50	No conditions

*95% CI for RRs determined using Wald method.

For each criterion, it is necessary to have all the features described in the column headings in order for the event to be considered to have achieved that particular criterion. Events may meet more than one criterion. Events that meet at least one of the criteria are shortlisted as a potential AR.

Based on 310 participants being exposed to Gepotidacin, there is a 90% chance of observing at least one particular adverse event if the true incidence rate of that adverse event is not below 0.75%. When the active control arm has zero events, the estimate of relative risk (RR) would be undefined and therefore cannot be evaluated using the quantitative screening criteria given above. The screening criteria in this case will be based on the minimum number of subjects with the event of interest in gepotidacin arm (vs 0 in ceftriaxone plus azithromycin arm). At least 3 participants with the AE of interest must be observed in the gepotidacin arm in order to be included in the “short list” of potential ARs.

A summary table of treatment emergent adverse events by SOC, HLTs and PTs with incidence (%) for each treatment group, RR and the associated 95% CI will be generated. An additional table will be produced displaying only the adverse events meeting the pre-specified quantitative screening criteria.

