- k. At Follow-up, a pharyngeal specimen will be collected for detection of NG and CT by NAAT from participants whose NAAT assay had the presence of nucleic acid for NG at both Baseline and TOC. NAAT assay results will be available to the study sites by the Follow-up Visit.

Table 7 BTZ116577 NAAT Overview by Body Site and Organism

Body site	Organism	Baseline Visit			TOC Visit		F/U Visit	
		Local Lab	Central Lab		Central Lab		Central Lab	
			Real Time	Batch	Real Time	Batch	Real Time	Batch
Urogenital	NG/CT	X	X		X			
	MGen			X				X ^b
Pharyngeal ^a	NG/CT		X		X		X ^c	
Rectal ^a	NG/CT		X		X			

NG = *N. gonorrhoeae*; CT = *C. trachomatis*; MGen = *M. genitalium*; RT = real time (processed upon arrival); F/U=Follow-up.

a. Optional (upon patient consent)

b. Only if positive NAAT at baseline visit. MG NAATs will be run weekly by the central lab, so that baseline and results are back to the site in time for F/U.

c. Only if positive NG NAAT at baseline and TOC visit. Sites will have baseline and TOC pharyngeal NAAT results back by F/U

Note: Only central laboratory NAAT results will be used in the exploratory analysis, local lab NAAT is conducted to guide therapy at the TOC visit (*Chlamydia trachomatis*)

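### The SAP flags treatment-emergent AEs by start date alone, so infections already present in pre-dose Baseline specimens can be counted as treatment-emergent when the result arrives after dosing

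*Protocol*

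**What the plan says.** **Protocol Appendix 4 (Section 12.4)** says two things. Among events that meet the AE definition it lists "New conditions detected or diagnosed after study treatment administration even though it may have been present before the start of the study". Just above, it defines the treatment-emergent subset: "A treatment-emergent AE is an event that emerges during treatment having been absent pretreatment or worsens relative to the pretreatment state".

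**Protocol Section 9.2.1** sends onsets between consent and dosing elsewhere: such an occurrence "will be recorded on the medical history/current medical conditions section of the eCRF and not the AE section". **Protocol Section 9**, under the Baseline Visit, adds: "Any pre-existing conditions, signs and/or symptoms present prior to the first dose of study treatment will be recorded in the eCRF".

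**SAP Section 8.1** uses a date rule only: "A treatment emergent AE (TEAE) is defined as an AE with start date/time after the first dose date/time of the study treatment". AEs that start before the first dose are listed but not summarised. The treatment-emergent flag in **SAP Appendix 2** (the second section numbered 12.2.1) is also a date rule, but counts onset *on or after* the start of treatment rather than *after* it. Both compare dates only when a time is missing. SAP Section 12.5.2.1 treats an AE with an entirely unknown start date as treatment-emergent.

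**The concern.** The schedule makes late reporting of an existing condition routine. Every participant gives pre-dose urogenital specimens for chlamydia and *M. genitalium* NAAT, and dosing follows at the same visit. SAP Table 7 says "MG NAATs will be run weekly by the central lab", with results due back by Follow-up. It also says that the local chlamydia NAAT is used to guide therapy at Test-of-Cure. HIV and hepatitis serology is drawn before dosing and tested centrally. No turnaround is stated for serology, so a post-dose result there is an inference from same-visit dosing.

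Under the Appendix 4 bullet, a site may properly enter such a finding as an AE. Under Sections 9 and 9.2.1, another site may properly enter it as medical history. The protocol's treatment-emergent definition would remove it at analysis, but the SAP does not apply that definition.

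Treatment-emergent AEs are a secondary endpoint, reported as a proportion in each arm. The any-AE relative risk is also a planned benefit/risk display (SAP Section 10).

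**Working it through.** **1. One finding under each rule.** Take a participant dosed on Day 1 whose pre-dose specimen is positive, with the result received some days later and entered as an AE.

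| Start recorded as | Protocol definition | SAP 8.1 (*after*) | SAP Appendix 2 (*on or after*) |
|---|---|---|---|
| Result date | Not emergent unless it worsens | Emergent | Emergent |
| Specimen date, pre-dose time | Not emergent | Not emergent | Not emergent |
| Specimen date, no time | Not emergent | Not emergent | Emergent |
| Unknown | Not emergent | Emergent (12.5.2.1) | Emergent (12.5.2.1) |

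The third row matters for the fix. Specimen and dose share a calendar day, so dating to the specimen is not enough under Appendix 2 when no time is recorded.

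**2. The SAP's own figure.** Section 8.5.2 gives a 90% chance of seeing at least one case of an AE with true incidence 0.75% among 310 gepotidacin participants. 1 − (1 − 0.0075)^310 = 0.903, which agrees. The 310 is half of about 620 randomised 1:1.

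**3. Dilution of the any-AE relative risk.** The documents give neither AE rates nor co-infection prevalence, so every rate here is an assumption. Let *g* and *c* be the AE rates without these infections. Let *b* be the share of each arm with such an infection recorded as a post-dose AE, equal in both arms and independent of other AEs.

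Observed RR = [1 − (1 − g)(1 − b)] / [1 − (1 − c)(1 − b)]

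| b | g = 40%, c = 20% (true RR 2.00) | g = 30%, c = 20% (true RR 1.50) |
|---|---|---|
| 2% | 0.412 / 0.216 = 1.91 | 0.314 / 0.216 = 1.45 |
| 5% | 0.430 / 0.240 = 1.79 | 0.335 / 0.240 = 1.40 |
| 10% | 0.460 / 0.280 = 1.64 | 0.370 / 0.280 = 1.32 |

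The risk difference shrinks only by the factor (1 − b): at 40% v 20% and b = 10%, from 20 to 18 percentage points. The arm proportions rise from 40% to 46% and from 20% to 28%.

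**4. The adverse-reaction screen.** Two independent Binomial(310, p) counts with equal p were put through the SAP 8.5.2 criteria, including the rule of at least 3 v 0. A single balanced High Level Term is shortlisted by chance with probability 33.3% at p = 1%, 16.1% at 5%, 18.4% at 10% and 8.6% at 20%. The confidence-interval criterion alone gives at most about 2.4%.

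**The case against.** The best defence is that the safeguards already exist. The protocol's definition excludes pre-existing conditions, Section 9.2.1 sends pre-dose onsets to medical history, and SAP 8.1 keeps pre-dose starts out of the summaries. SAP 6.1.2 summarises pre-treatment chlamydia and *M. genitalium* NAAT and serology as baseline characteristics, and SAP 5.4.2 makes co-infection and HIV status subgroups. Miscounting needs a site to enter the result date, and no text tells it to. Broad capture at sites with filtering at analysis is a defensible policy.

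Most of this stands, and it puts the gap in the SAP rather than in the Appendix 4 bullet. It does not close the gap, because the filter is what the SAP leaves out. Section 9.2.1 literally covers onsets after consent, not infections acquired earlier. The Baseline history rests on interview and records, which cannot show a result not yet reported.

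A reader might infer more, but the documents do not support it:

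- **That Appendix 4 by itself makes these findings treatment-emergent.** Its own definition says otherwise.
- **That false adverse-reaction signals follow.** "Events that meet at least one of the criteria are shortlisted as a potential AR" applies to every balanced term, and the rates in step 4 come from point-estimate criteria. SAP 8.5.1 calls the screen an aid to medical judgment, and a causality review follows (8.5.3).
- **That recording would differ by arm because only the comparator contains azithromycin.** Treatment of positives is directed in both arms, and Protocol Section 5.4 says that the study regimen may be insufficient for *M. genitalium*. Nothing indicates how often sites in either arm would enter an AE, so no figure can be attached.
- **That the Baseline ECG is affected too.** It is an eligibility test reviewed before randomisation.

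**Conclusion.** The inconsistency is real and should be corrected, but its reach is small. Infections present before dosing can enter the treatment-emergent tables through a date-only flag that departs from the protocol's definition. Whether they do depends on which date the site enters.

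The effect is limited to spurious infection terms, raised any-AE proportions and an any-AE relative risk pulled towards 1. The step 3 figures are upper-end illustrations on assumed rates: *b* is the share actually recorded as post-dose AEs, which would equal prevalence only if every positive were entered that way.

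Relative risks by preferred term, by High Level Term and for AEs of special interest are not diluted for drug-caused events. The primary efficacy analysis is untouched.

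**What to change.** In SAP 8.1 and the Appendix 2 treatment-emergent flag:

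- Add the protocol's requirement that the event be absent before treatment or worsen afterwards.
- State that a condition identified from a pre-dose specimen takes the specimen date/time as onset. It is not treatment-emergent unless it worsens, even if no time is recorded. SAP 5.2 already presumes untimed Day 1 assessments to be pre-dose.
- Use one boundary, *after* or *on or after*, in both places.
- Before unblinding, check infection AEs programmatically against Baseline NAAT and serology results.

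In Protocol Appendix 4, a cross-reference reconciling the bullet with the treatment-emergent definition and Section 9.2.1 is enough. The AE-collection bullet need not be narrowed.

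The cost is a few sentences and one blinded check on data already held. The downside is that some site-entered AEs move from the treatment-emergent summaries to the listings only.
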